#### 8.1. EFFICACY ENDPOINTS AND ANALYSES

The ITT population will be used for the efficacy analysis. Patients will be analyzed according to randomized treatment group. The changes within each treatment group and the overall change from baseline in continuous efficacy variables will be estimated using an MMRM. Although the focus of this study is to describe the within-group changes, the differences between the treatment groups will be estimated as well, but no inferential analyses regarding the between-group differences will be done. The model will include visit, stratification variables (Hoehn and Yahr stage and screening FEV1 and/or FEV1/FVC), treatment group, treatment/study group, and the interaction between the treatment group and visit as fixed factors as fixed factors. The baseline value will be used as a covariate. An unstructured covariance structure will be applied for the MMRM. In case the model will not converge with the unstructured covariance structure, the heterogeneous compound symmetry (CSH) or the heterogeneous Toeplitz structure (TOEPH). If the unstructured covariance structure will be used, the denominator degrees of freedom will be computed using the Kenward-Roger method. In

## Statistical Analysis Plan

case of other covariance structures, the BETWITHIN option will be used for the denominator degrees of freedom.

For all patients, categorical data will be evaluated descriptively. Each visit will be evaluated separately for the categorical endpoints. The efficacy endpoints and associated analyses are as follows. For the detailed definition of the endpoints, see Section 4.3.

- Resolution of an OFF to an ON state within 60 minutes after study drug is administered in the clinic and maintaining the ON at 60 minutes after study drug administration (per the examiner's subjective assessment). This endpoint will be based on the examiner's subjective assessment. The proportions of patients will be summarized descriptively for each CVT-301 treated patients. The missing values will be counted as non-resolved. The data will be summarized with descriptive statistics within each treatment group and overall. The GLIMMIX procedure for binomial data with logit link will be used to estimate the treatment group difference. Factors similar to the ones used described above will be included in the model (sensitivity method). An unstructured covariance structure will be used. The missing data will not be imputed as non-responders in this sensitivity analysis. Below sample code will be used for analysis.

```
proc glimmix data=t2212;
class pdsevbl fev1bl trtpn avisitn stdygrp usubjid;
model avalc(event='Y')= updooffsc pdsevbl fev1bl stdygrp trtpn avisitn trtpn*avisitn/s dist=binomial link=logit cl
oddsratio (diff=first) solution;
random avisitn/subject=usubjid residual type=un ;
lsmeans avisitn*trtpn/ cl ilink;
ods output tests3=PVAL lsmeans=lsmeans(keep=trtpn avisitn mu) estimates=estimates(keep=statement label
expeestimate explover expupper);
/* tv4 */
estimate "tv4 trt 2 vs 1" trtpn -1 1 trtpn*avisitn 0 0 0 -1 0 0 0 0 1 0 /cl or e;
run;
```

- Change from baseline (3 consecutive days prior to TV1) in patient-recorded total daily OFF time, assessed by the patient and recorded in the PD Diary for 3 consecutive days prior to the visit. Similar methods as for primary endpoint will be used. The baseline daily OFF time will be used as a covariate in the MMRM. Only valid diary days will be included in the diary summarizations. In addition, change from baseline in total daily ON time without dyskinesia, total daily ON time with non-troublesome dyskinesia and total daily ON time with troublesome dyskinesia will be analyzed similarly using the MMRM. For the total daily OFF time only, MI analysis will be performed as a sensitivity analysis and subgroup analysis on subgroups in [section 6.6](#) will also be prepared.
- The PGI-C score. The proportions of patients who improved (much improved, improved or a little improved) will be tabulated by visit for CVT-301 treated

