11.1.12. Other Safety Assessments

11.1.12.1. UPDRS Part 4 and Examiner-Rated Dyskinesia

The UPDRS Part 4 is an assessment of potential complications of PD therapies. Questions 32-35 (related to dyskinesias) and 36-39 (related to clinical fluctuations) only will be completed as indicated in the time and events tables in [Appendix 2](#) through [Appendix 10](#). The baseline assessment for CVT-301-naïve and [CVT-301-009](#) patients will be completed at TV1. The baseline assessment for [CVT-301-004](#) patients will have been completed at TV1 of [CVT-301-004](#) study.

Additionally, during the post-dosing follow-up period at TV2, TV3, TV4, TV5, and TV6, the examiner will observe the patient for the appearance of dyskinesia during the 60-minute post-dose period and the maximum severity (mild, moderate, or severe) of any dyskinesia in the 60-minute post-dose period will be noted in the eCRF. The examiner will also note if the patient converts to the ON state during the 60-minute post-dose period and if so, whether the patient is still in the ON state at 60 minutes post-dose.

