## Statistical Analysis Plan

impute missing values based on a sequential procedure reflecting the monotone missing data pattern. Patients with the first missing value occurring at visit at Month 1 will have their missing Month 1 value replaced by an imputed value from a regression model with baseline value, treatment group, treatment/study group and the stratification factors as explanatory variables. In the next step, patients with their Month 3 value missing will have their missing Month 3 value replaced by an imputed value from a regression mode with baseline value, treatment group, treatment/study group and stratification factors and the Month 1 value as explanatory variables. Similar procedure will be used to replace the missing values at Month 6, 9 and 12.

The imputed datasets generated with the approach described above do contain only non-missing values and are used as input in the model for the exploratory efficacy endpoint. MMRM models similar as described above will thus be run on each of the generated imputed datasets. Finally, the MIANALYZE procedure in SAS will be applied to combine the results from these several datasets to derive an overall estimate of the within-group changes.

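### The SAP 8.1 GLIMMIX contrast labelled tv4 falls on the fourth of five analysis visits, Month 9, and not on Month 6

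*SAP*

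**What the plan says.** SAP 8.1 analyses resolution of OFF to ON within 60 minutes in two ways. The main summary is descriptive, with missing values counted as non-resolved. A GLIMMIX logit model is then named as the sensitivity method: "The missing data will not be imputed as non-responders in this sensitivity analysis". The code is introduced with "Below sample code will be used for analysis".

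The relevant parts of that code are:

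- The CLASS list: "class pdsevbl fev1bl trtpn avisitn stdygrp usubjid".
- One ESTIMATE statement, commented and labelled tv4 for treatment 2 versus 1, with `trtpn -1 1` and then "trtpn*avisitn 0 0 0 -1 0 0 0 0 1 0".
- An ODS OUTPUT line that keeps the ESTIMATE label together with the exponentiated estimate and its limits.

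On timing, Protocol 11.1.12.1 has the examiner record dyskinesia and conversion to ON "during the post-dosing follow-up period at TV2, TV3, TV4, TV5, and TV6". SAP 3.8 places TV4 at Week 24 and TV5 at Week 36. The pooling table in SAP 8 gives post-baseline analysis visits at Months 1, 3, 6, 9 and 12.

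**The concern.** An ESTIMATE statement selects visits by position, not by name. Here the label says TV4, but the coefficients sit in the fourth visit slot. Those would agree only if the first slot were TV1, and the endpoint starts at TV2.

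This is the only explicitly labelled, visit-specific dose contrast in the code, and the only odds ratio that the ODS OUTPUT line saves. If it selects the wrong visit, Table 14.2.1.2 would show one visit's dose comparison under another visit's name. Nothing in the number itself would reveal it.

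**Working it through.** **1. Column order.** `trtpn` precedes `avisitn` in CLASS, so visit varies fastest within dose. Ten coefficients are 2 doses × 5 visits. Treatment 1 is taken as DL1 and treatment 2 as DL2.

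| Position | 1 | 2 | 3 | 4 | 5 | 6 | 7 | 8 | 9 | 10 |
|---|---|---|---|---|---|---|---|---|---|---|
| Dose | DL1 | DL1 | DL1 | DL1 | DL1 | DL2 | DL2 | DL2 | DL2 | DL2 |
| Analysis month | 1 | 3 | 6 | 9 | 12 | 1 | 3 | 6 | 9 | 12 |
| Coefficient as printed | 0 | 0 | 0 | −1 | 0 | 0 | 0 | 0 | +1 | 0 |
| Needed for Month 6 | 0 | 0 | −1 | 0 | 0 | 0 | 0 | +1 | 0 | 0 |

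The printed contrast is DL2 minus DL1 at Month 9.

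**2. Why five levels, and which.** The assessment schedule gives TV2 to TV6. The TV1 tables (Protocol Appendices 4 and 5) have no row for monitoring dyskinesia and ON/OFF states. The pooling table gives five months, and the OFF-time imputation text in SAP 8.1 agrees: after Months 1 and 3, "Similar procedure will be used to replace the missing values at Month 6, 9 and 12". Under either list the fourth level is not TV4 at Week 24. It is TV5 if visits are not pooled and Month 9 if they are.

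**3. Estimability.** The statement gives no `avisitn` coefficients, so the interaction coefficients must sum to zero within each visit, to −1 over DL1 and to +1 over DL2. At the fourth level −1 + 1 = 0, and the dose sums are −1 and +1. The contrast is therefore estimable, and SAS would return a result without complaint.

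**4. Other codings.**

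- Six levels, TV1 to TV6: −1 falls on (DL1, TV4) and +1 on (DL2, TV3). The visit sums are not zero, so the contrast is not estimable.
- Dose varying fastest: not estimable for any of the visit lists tried.
- Four levels: only 8 cells for 10 coefficients.
- Five levels, TV1 to TV5: matches the label, but uses a visit where the endpoint is not collected and drops TV6, where it is.

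**5. Which clinic visit Month 9 is.** The pooling table carries the 004E Month 3 to 9 visits of patients given CVT-301 in study 004 forward as Months 6 to 12.

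| Source group | Month 6 | Month 9 | Month 12 |
|---|---|---|---|
| CVT-301 in study 004 | 004E TV3 | 004E TV4 | 004E TV5 |
| Placebo in 004, naïve, 005 observational arm | 004E TV4 | 004E TV5 | 004E TV6 |

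**6. Numerical consequence.** This depends on how the dose effect changes between the two months, for which the documents give no figures. As an assumption, take 50% response on DL1 throughout and 55% on DL2 at Month 6, and ignore covariates. The Month 6 odds ratio is (0.55/0.45)/(0.50/0.50) = 1.22. The code returns the Month 9 value:

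| Assumed DL2 response at Month 9 | Odds ratio returned |
|---|---|
| 50% | (0.50/0.50)/1 = 1.00 |
| 55% | (0.55/0.45)/1 = 1.22 |
| 60% | (0.60/0.40)/1 = 1.50 |
| 65% | (0.65/0.35)/1 = 1.86 |

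If the odds ratio is the same at both months, only the label is wrong.

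**The case against.** Several points on the other side are sound.

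- **Pooling.** A reader might infer that the code simply reports TV5 as TV4. The SAP 8 table does not support that for everyone: for patients treated in study 004, the Month 9 level is physically 004E TV4. This limits how the error should be described but does not rescue the label, since the pooled level is Month 9 for all groups and mixes TV4 and TV5.
- **Not the only odds ratio.** The MODEL statement also requests odds ratios, and LSMEANS gives each dose's estimated response at every visit. The planned table is by visit, so the printed line looks like a template. A reader might go on to infer that every visit's contrast is shifted, but the SAP prints no other line.
- **Small reach.** The model is a sensitivity analysis, and SAP 8.1 rules out inferential analysis of between-group differences.
- **It could be caught.** The ESTIMATE carries the `e` option, which prints the coefficients, and SAP 13 commits to checking program logic and output. That makes detection possible, but does not make the specification right.
- **The coding is not printed.** This is the strongest point. If `avisitn` carried a text format sorted alphabetically (Month 1, Month 12, Month 3, Month 6, Month 9), the fourth level would be Month 6. No such format appears in the SAP, and the variable name has the usual suffix for a numeric code, in contrast to `avisit` in the SAP 9.1 code.

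**Conclusion.** The label and the coefficients disagree. Run as printed, the contrast compares the doses at Month 9 and files the result under TV4, a displacement of one analysis visit. This rests on one assumption, that `avisitn` has the five analysis visits in default ascending order. The coefficient count, the assessment schedule and the pooling table all support five levels, but the SAP does not state the coding.

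The point should be corrected before the code is run, and its reach is narrow. A reader might infer that the efficacy conclusions or the main result for this endpoint are compromised. The documents do not support that: the descriptive proportions (Table 14.2.1.1), the LS-means by visit and the primary spirometry analysis do not use this statement.

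**What to change.** Choose one of two changes to the ESTIMATE statement in SAP 8.1:

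- for the Week 24 comparison, use `trtpn -1 1 trtpn*avisitn 0 0 -1 0 0 0 0 1 0 0`, labelled Month 6; or
- keep the printed coefficients and relabel the contrast Month 9.

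In either case, label contrasts by pooled analysis month and not by TV number, and state the `avisitn` values and their sort order. Keeping a TV4 label on the corrected coefficients would still be wrong for patients treated in study 004, whose Month 6 is 004E TV3.

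Preferably, drop hand-coded positions and use `lsmeans trtpn*avisitn / slicediff=avisitn oddsratio cl ilink`, which gives the dose odds ratio at every visit and suits the by-visit layout of Table 14.2.1.2. The ODS OUTPUT line would then need to save those differences.

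The cost is a line or two of SAS and a sentence in the SAP. No data, endpoint or design element changes.

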## Statistical Analysis Plan

patients. This summary will be complemented by the distribution of each response category (much improved, improved, a little improved, no change, a little worse, worse, much worse) tabulated by the treatment group. The data will be summarized with descriptive statistics within each treatment group and overall.

- Changes from baseline in endpoints based on S&E ADL score, UPDRS Part 2 score, PHQ-9 total score, and PDQ-39 sub-scores and index score. An ANCOVA model with the treatment group, treatment/study group and stratification variables as fixed factors and the baseline value as a covariate will be used to estimate the treatment group differences. In addition, the data will be presented with descriptive statistics classified by treatment group and visit. The observed cases will be used in the analysis and summaries.
- Change from baseline (TV1) and Last Day of Treatment (LDOT) to days 1, 3, 6, 8, 11, 14, 17, 24, and 28 after TV6 in the PHQ-9 will be summarized descriptively. LDOT is defined as assessment taken on TV6 or ET for patients who didn't enrolled into the sub-study and TV4, TV5 or TV6 for patients who enrolled into sub-study.

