10.1.5. Early Withdrawal Visit

Patients who withdraw prematurely will complete the TV6 assessments (see [Section 10.1.3.9](#)), except for the pre-TV6 DLco and spirometry assessments, at the time of withdrawal. In addition, patients will be scheduled the DLco and spirometry visit 4 to 5 weeks after completion of the Early Withdrawal Visit. The DLco and spirometry assessments should be performed in an ON state (as reported by the patient to the pulmonary technician) in the pulmonary function facility. As part of the procedure, a slow vital capacity maneuver will be first, followed by DLco, and then spirometry. Patients who withdraw prematurely and prior to participating in the sub-study to assess potential withdrawal symptoms will complete the withdrawal assessments during the 28 days following completion of the TV6 assessments (see [Section 10.1.4](#)).

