12.6. Efficacy Analysis

The derivation of the efficacy variables will be defined in detail in the SAP.

All patients who are enrolled in CVT-301-004E and who receive at least 1 dose of CVT-301 will be included in the efficacy analyses as well but will be grouped according to the randomized treatment.

The data for patients who were enrolled in the [CVT-301-004](#) study, the [CVT-301-009](#) study and for the CVT-301-naïve patients study will be primarily analyzed together, while the patients who were enrolled in the [CVT-301-003](#) study will be analyzed separately. A sensitivity analysis will be performed for the patients who enrolled in the [CVT-301-004](#) study separately and for the CVT-301-naïve patients separately.

The changes within each dose level and the overall change from baseline in continuous efficacy variables will be estimated using an MMRM. Although the focus of this study is to describe the within-group changes, the differences between the dose levels will be estimated as well, but no inferential analyses regarding the between-group differences will be done. The model will include the treatment group (CVT-301 DL1 or CVT-301 DL2), visit, the stratification variables (Hoehn and Yahr disease severity scale rating and screening FEV1 and/or FEV1/FVC) and the interaction between the treatment group and visit as fixed factors. The baseline value will be used as a covariate, if available. The categorical data will be primarily evaluated descriptively. Each visit will be tested separately.

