## Statistical Analysis Plan

- For the primary analysis of spirometry and selected efficacy endpoints, likelihood-based modeling approach will be used to handle incomplete data. For this purpose, Mixed Model for Repeated Measures (MMRM) will be applied (see [Section 8.1.](#))
- Sensitivity analysis for spirometry and selected explorative efficacy endpoints will be conducted using the Multiple Imputation (MI) approach, i.e. by replacing each missing value with a set of plausible values that represent the uncertainty about the right value to impute, see [Section 9.1.](#)
- For the binary explorative efficacy endpoints, sensitivity analyses will be conducted using worst case imputation, where visits with missing data are counted as non-resolved (primary method), see [Section 8.1.](#)
- For AEs, the overall incidence of TEAEs, normalized for duration of exposure will be calculated to account for the shorter follow-up time in patients who discontinue the study prematurely, see [Section 9.4.](#)

The Safety and ITT population will be used for the analysis of the primary and secondary endpoints. This population includes all patients enrolled to study CVT-301-004E who received at least 1 dose of inhaled CVT-301, regardless of whether they have post-baseline data or not for the variable in question. The patients with no post-baseline data will not contribute to the analyses performed with the MMRM approach, but they do contribute to the sensitivity analyses using the MI approach. Due to this, no additional population, like a modified ITT population including only the patients with post-baseline will be defined.

Safety data (other than the primary endpoint) will not be subjected to any imputation and will be summarized on an observed case basis.

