### 6.4. VISIT WINDOWS

The visits recorded in database will be used for all analyses. There is no plan to re-assign visits based on actual visit dates.

For the patients who discontinue the study prematurely, a set of assessments is scheduled to be performed at the ET visit (PDQ-39, PHQ-9, PGI-C, UPDRS Part 2, UPDRS Part 4, S&E ADL score and safety assessments). The following rules will be used to analyze the data collected at the ET visit:

- For the PDQ-39, PHQ-9, PGI-C, UPDRS Part 2, UPDRS Part 4 and S&E ADL score, the data from the ET visit will be re-assigned to TV6 in case there is no TV6 assessment.

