### Exploratory analyses of the efficacy data

- Changes from baseline in endpoints based on S&E ADL score, UPDRS Part 2 score, PHQ-9 total score, Impact of Parkinson's OFF Episodes Patient Survey score along with numeric individual score (i.e. Impact of OFF Time on Disability - ON State Disability and Impact of OFF Time on Disability - ON State Disability), and PDQ-39 sub-scores and index score. An ANCOVA model with the treatment group, treatment/study group and stratification variables as fixed factors and the baseline value as a covariate will be used to estimate the treatment group differences. In addition, the data will be presented with descriptive statistics classified by treatment group and visit. The observed cases will be used in the analysis and summaries.
- For Impact of Parkinson's OFF Episodes Patient Survey, the frequency and percentage of patients for each response will be summarized by treatment group and overall for each of the item within each section.

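### SAP 8.1 assigns MMRM to continuous efficacy variables, then gives four rating scales and the OFF-episode survey score an undeclared observed-case ANCOVA for dose differences only

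*SAP*

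**What the plan says.** **The general rule.** Protocol 12.6 states: "The changes within each dose level and the overall change from baseline in continuous efficacy variables will be estimated using an MMRM". The opening of SAP 8.1 repeats it: the "overall change from baseline in continuous efficacy variables will be estimated using an MMRM". It sets out the model: visit, strata, treatment group, treatment/study group, treatment-by-visit interaction and baseline, with an unstructured covariance. It also says that the study's focus is within-group change and that dose differences are estimated without inference.

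**The exception.** Further down SAP 8.1, S&E ADL, UPDRS Part 2, PHQ-9 and PDQ-39 get "An ANCOVA model with the treatment group, treatment/study group and stratification variables as fixed factors and the baseline value as a covariate", used for the difference between doses. Visit is not in the model and there is no repeated effect. The entry closes: "The observed cases will be used in the analysis and summaries". The exploratory list at the end of the section repeats the entry and adds the survey: "Changes from baseline in endpoints based on S&E ADL score, UPDRS Part 2 score, PHQ-9 total score, Impact of Parkinson's OFF Episodes Patient Survey score".

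**Related rules.**
- SAP 6.3: "For the primary analysis of spirometry and selected efficacy endpoints, likelihood-based modeling approach will be used to handle incomplete data". The selected endpoints are not named there; the text points back to SAP 8.1.
- Protocol 10.1.5: "Patients who withdraw prematurely will complete the TV6 assessments" when they leave, apart from the pulmonary tests due before TV6.
- SAP 6.4, for PDQ-39, PHQ-9, UPDRS Part 2 and S&E among others: "the data from the ET visit will be re-assigned to TV6 in case there is no TV6 assessment".
- SAP 11 lists one departure from the protocol, the handling of study 003 and 009 patients.

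**The concern.** Two statements in one SAP section give the same endpoints different models, and SAP 11 does not say that one was meant to replace the other. The choice has consequences. An observed-case ANCOVA at a visit uses the baseline and that visit's value only. The MMRM also uses the visits a patient attended before leaving, so it remains valid if dropout depends on those earlier scores. The ANCOVA does not, in general.

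The ANCOVA also misses the aim that SAP 8.1 sets itself. It is there to compare doses, so within-group change in these scales is left to raw observed-case summaries. Nor does the text say outright that the ANCOVA is fitted visit by visit. The table titles in SAP 14 suggest that it is, but a single fit to stacked visits would treat repeated rows from one patient as independent.

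**Working it through.** **1. Models side by side**

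| Endpoint | Model | Missing-data sensitivity analysis |
|---|---|---|
| Daily OFF time (SAP 8.1) | MMRM | Multiple imputation |
| Three ON-time diary measures (SAP 8.1) | MMRM | None |
| UPDRS Part 4 (SAP 9.12) | MMRM, as for spirometry | None |
| S&E, UPDRS Part 2, PHQ-9, PDQ-39 (SAP 8.1, listed twice) | ANCOVA, observed cases | None |
| OFF-episode survey score (SAP 8.1, exploratory list) | ANCOVA, observed cases | None |

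UPDRS Parts 2 and 4 are collected together at TV2 to TV6 yet get different models, with no reason given.

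**2. Who contributes at each visit**

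This combines the early-termination (ET) rule of SAP 6.4 with the visit-pooling table in SAP 8.

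- *Former 004 placebo, naïve and 005 patients.* Months 1 to 9 rest on those who attended. Month 12 is TV6, so it also holds ET values of leavers, dated whenever they left.
- *Patients given CVT-301 in study 004.* Months 1 and 3 come from study 004, which they had to complete. Months 6, 9 and 12 are the 004E Month 3, 6 and 9 visits. Their TV6 is not used, so on a literal reading an ET value moved to TV6 drops out.
- *Survey score.* It is not in the SAP 6.4 list, and the last rule there discards other ET data.

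**3. Attrition implied by the plan**

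The inputs are 390 enrolled and about 290 completers (protocol 12.1, SAP 3.5).

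(390 − 290)/390 = 100/390 = 0.256, or 25.6%.

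SAP 3.5 says the number is not formally calculated, so there is no sample-size formula to reproduce. The rate is for the whole study. It includes 003 and 009 patients, whom SAP 5.3 removes from the efficacy population.

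**4. Size, simple form**

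Shift of a stayers-only mean = share missing × gap between stayers and leavers. The gap is assumed.

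| Gap (SD) | 0.10 | 0.25 | 0.50 | 1.00 |
|---|---|---|---|---|
| 0.256 × gap (SD) | 0.026 | 0.064 | 0.128 | 0.256 |

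**5. Size, by simulation**

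Assumed: n = 390, five visits, correlation 0.7 between any two visits, and dropout near 25.6% driven by the last observed score. Mean improvement fades from 0.30 SD to 0.15 SD. There were 400 trials per setting. Entries are bias in the last-visit mean change, in SD; negative means too favourable.

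| Log-odds of dropout per SD worse | 0 | 0.5 | 1.0 |
|---|---|---|---|
| Dropout obtained | 25.3% | 26.6% | 25.9% |
| ANCOVA, no ET data, at all-patient baseline mean | 0.000 | −0.030 | −0.057 |
| ANCOVA, no ET data, at baseline mean of those observed | 0.000 | 0.002 | 0.001 |
| Likelihood estimate (MMRM type) | 0.000 | 0.001 | 0.000 |
| Observed mean with ET values at last visit | −0.029 | 0.005 | 0.034 |

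Rows two and three differ because, with equal correlations, selective dropout shifts baseline and final scores alike. The ANCOVA bias therefore depends on where the adjusted mean is evaluated. The last row is off even when dropout is uninformative, because ET values date from earlier visits with larger mean improvement.

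**6. Dose difference**

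Bias in the difference = bias in one dose − bias in the other. It is zero if dropout acts alike in both. If one dose had slope 0.5 and the other 1.0, it would be 0.057 − 0.030 = 0.027 SD.

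**The case against.** The other side has five good points.

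- **The SAP can be read as consistent.** SAP 6.3 limits MMRM to selected endpoints and SAP 8.1 then goes endpoint by endpoint, so a programmer would probably run the ANCOVA. The SAP also overrides the protocol. This softens the conflict but does not remove it: both statements are in the SAP, the opening sentence was never narrowed, and SAP 11 is silent.
- **Leavers are not simply lost.** A reader might infer that all late-visit means for these scales rest on patients who stayed. SAP 6.4 and protocol 10.1.5 contradict that for TV6 in every group whose TV6 is used. If all leavers attended an ET visit, TV6 would be complete and an MMRM would have little to add there.
- **The ANCOVA compares two active doses.** A reader might infer that it flatters the drug. Bias common to both doses largely cancels in that contrast, and no inference is planned on it. Only the within-group changes are exposed.
- **MMRM is no cure-all.** It too uses observed values only, relies on MAR, and would treat an ET value placed at TV6 as a true Month 12 value.
- **The stakes are modest.** The primary objective is pulmonary safety. These are secondary scales, also listed as exploratory, with no bearing on sample size or alpha.

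All five stand as limits on the point. None supplies a reason for the different model, a missing-data sensitivity analysis, or the model-based within-group estimates that SAP 8.1 calls its focus.

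**Conclusion.** The inconsistency holds and depends on no simulation. SAP 8.1 names two models for the same endpoints, does not declare the departure, and leaves these scores without a missing-data sensitivity analysis.

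For the four scales, the stayers-only problem is confined to visits missed before TV6 and to Month 12 in patients given CVT-301 in study 004. In the other groups, the Month 12 problem is that ET values of any date count as Month 12. The survey score has no ET rescue in any group.

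The size cannot be fixed from the documents, which give no SD and no dropout model. Under the assumptions above, the baseline-adjusted bias without ET data is about 0.03 to 0.06 SD at the all-patient baseline mean. It is near zero at the observed patients' baseline mean, and smaller between doses when dropout acts similarly in both. A reader might infer a large gain for the drug from attrition of 25.6%; that would need a large unstated gap between leavers and stayers and would have to ignore SAP 6.4. This is a worthwhile, inexpensive correction to secondary analyses and does not threaten the main conclusions.

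**What to change.** 1. In both places in SAP 8.1, replace the ANCOVA for S&E ADL, UPDRS Part 2, PHQ-9, PDQ-39 and the survey score with the MMRM defined at the start of that section.
2. Report within-group least-squares mean changes by visit with 95% intervals, as well as the dose differences.
3. Keep the observed-case descriptive tables.
4. Run the TV6 analysis with and without the re-assigned ET values. State what happens to those values where TV6 is not used, and whether the survey score's ET values are meant to be discarded.

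If the sponsor prefers to keep the ANCOVA, the minimum is to name in SAP 8.1 which endpoints use which model, say that the ANCOVA is fitted at each visit, and enter the change in SAP 11.

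The cost is SAP wording and a little programming, since the model is already specified. Reliance on MAR remains. SAP 2 labels analyses defined after the unblinding of study 004 as exploratory. Protocol 12.6 already names MMRM for these variables, so the change returns to a stated method.
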